9.1.5. New-Onset Chronic Illness

An NCI is an AE that is new (ie, not present at baseline) and typically chronic. Because of the significance of this designation for the patient's health and for evaluation of vaccine safety, NCIs are expected to be diagnoses, not symptoms, and the Investigator should record sufficient data in the source document to support the diagnosis.

9.1.6. Immune-Mediated Medical Conditions (IMC)

A list of IMCs is provided in Appendix 2.

9.1.7. Serious Adverse Event

An AE or suspected adverse reaction is considered serious (an SAE) if, in the view of either the Investigator or Sponsor, it results in any of the following outcomes:

- Death
- Life-threatening (An AE is considered life-threatening if, in the view of either the Investigator or Sponsor, its occurrence places the patient or subject at immediate risk of death. It does not include an AE that, had it occurred in a more severe form, might have caused death.)
- Inpatient hospitalization or prolongation of existing hospitalization
- A persistent or significant incapacity or substantial disruption of the ability to conduct normal life functions
- A congenital anomaly/birth defect

Life-threatening means that the patient or subject was at immediate risk of death at the time of the SAE; it does not refer to a serious AE that hypothetically might have caused death if it were more severe. Hospitalization does not include same day surgery, elective surgery, optional admission not associated with a precipitating AE (ie, elective cosmetic surgery), or hospitalization planned before the start of the study for a pre-existing condition that has not worsened. Persistent or significant disability or incapacity means that there is a substantial disruption of a person's ability to carry out normal life functions.

Important medical events that may not result in death, be life-threatening, or require hospitalization may be considered serious when, based upon appropriate medical judgment, they may jeopardize the patient or subject and may require medical or surgical intervention to prevent one of the outcomes listed in this definition. Examples of such medical events include allergic bronchospasm requiring intensive treatment in an emergency room or at home, blood dyscrasias or convulsions that do not result in inpatient hospitalization, or the development of drug dependency or drug abuse.

9.2. Reporting Responsibilities and Periods

It is the responsibility of the Investigator or Subinvestigator(s) to perform periodic assessment of AEs. AEs spontaneously reported by the patient or reported in response to an open question from the study personnel (eg, 'Have you had any health problems since the previous visit/you were last asked?') or revealed by observation will be recorded.

AEs and concomitant medications will be recorded from the signing of informed consent to Day 169, but only MAEs, NCIs, and IMCs, which will be categorized as AEs, will be followed subsequently through Day 505. Concomitant medication collection will align with AE collection. The AE term, date of AE onset, date of AE resolution (if applicable), severity, causality, action taken for the AE, outcome and whether or not the AE is an MAE, NCI, and or SAE will be recorded.

AEs must be monitored until they are resolved or stabilized, are clearly determined to be due to a patient's stable or chronic condition or intercurrent illness(es), or follow-up is no longer possible. Data describing AEs will be recorded in the patient's medical record and as appropriate, an SAE report form. SAEs will be reported to the Sponsor as described in Section 9.7.

Any SAE that the Investigator considers to be possibly or probably related to study medication and occurs at any time after completion of the study must be reported to the Sponsor or designee. If at the time the Investigator initially reports an SAE, the event has not resolved, the Investigator must provide a follow-up report as soon as it resolves (or upon receipt of significant information if the event is still ongoing).

9.3. Assessment of Adverse Events

9.3.1. Severity

The Investigator should assess the severity of each AE. The AE will be recorded at its highest severity grade.

The severity of all AEs, both serious and non-serious, will be assessed by assigning a grade according to the FDA Guidance on the Toxicity Grading Scale for Preventive Vaccine Clinical Trials [United States Food and Drug Administration 2007]. NCI CTCAE, v 5.0 (http://ctep.cancer.gov/protocolDevelopment/electronic applications/ctc.htm) will be used for AEs not described in this guidance.

When an AE cannot be graded by the aforementioned FDA guidance or CTCAE, the following severity grading may be used:

- Grade 1 (Mild): awareness of sign or symptom, but easily tolerated
- Grade 2 (Moderate): discomfort enough to cause interference with usual activity
- Grade 3 (Severe): incapacitating with inability to work or do usual activity

- Grade 4 (Life-Threatening): refers to an event in which the patient was, in the view of the Investigator, at risk of death at the time of the event. (This category is not to be used for an event that hypothetically might have caused death if it were more severe.)
- Grade 5 (Fatal): death related to AE

An AE that is assessed as severe should not be confused with an SAE. Severity is a category for rating the intensity of an event, and both non-serious AEs and SAEs can be assessed as severe. An event will be defined as serious when it meets one of the criteria described in Section 9.1.7.

9.3.2. Relatedness (Causality)

The assessment of causality will be based on the information available and may be changed upon receipt of additional information.

Causality should be assessed using the following categories:

- Unrelated/Unlikely Related: clinical event with an incompatible time relationship to investigational agent administration, and that could be explained by underlying disease or other drugs or chemicals or is incontrovertibly not related to the investigational agent
- Possibly related: clinical event with a reasonable time relationship to investigational agent administration, and that is unlikely to be attributed to concurrent disease or other drugs or chemicals
- Probably related: clinical event with plausible time relationship to investigational agent administration, and that cannot be explained by concurrent disease or other drugs or chemicals

9.4. Safety Laboratory, Physical Examination, Electrocardiogram, and Vital Sign Abnormalities

Any abnormal laboratory result, physical examination finding, ECG interpretation, or vital sign measurement considered clinically significant by the Investigator will be recorded as an AE. A clinically significant laboratory abnormality is a confirmed abnormality (by repeat test) that is changed sufficiently from Screening/Baseline so that in the judgment of the Investigator a change in management is warranted. This alteration may include monitoring the laboratory test further, initiating other diagnostic tests or procedures, changing ongoing treatment, or administering new treatment.

Whenever possible, the underlying medical diagnosis (eg, anemia) will be recorded as the AE term. Repeated additional assessments required to establish the significance and etiology of an abnormal result should be obtained when clinically indicated.

9.5. Pregnancy

Pregnancy itself is not regarded as an AE unless there is a suspicion that the study medication may have interfered with the effectiveness of a contraceptive medication. Pregnancy in a patient's partner is not considered an AE. Congenital abnormalities/birth defects and spontaneous miscarriages should be reported and handled as SAEs. Elective abortions without complications should not be handled as AEs. The outcome of a pregnancy will be followed-up and documented even if the patient was withdrawn from the study. See Section 9.7.4 for further information on reporting of pregnancy.

An induced elective abortion to terminate a pregnancy without medical reason is not regarded as an AE. However, an induced therapeutic abortion to terminate a pregnancy because of complications or medical reasons must be reported as an SAE. The underlying medical diagnosis for this procedure should be reported as the SAE term. A spontaneous abortion in a study patient is always considered an SAE.

9.6. Overdose

Any instance of overdose (suspected or confirmed and irrespective of whether or not it involved study medication must be communicated to the Sponsor or a specified designee within 24 hours and be fully documented as an SAE. Details of any signs or symptoms and their management should be recorded including details of any antidote(s) administered.

An overdose of study medication is not expected, as it is administered via IM injection. Should patients receive a higher dose than the allocated dose, this should be reported in the eCRF and the Sponsor should be informed. Any deviations from the assigned dose will be handled as a protocol deviation.

9.7. Procedures for Recording and Reporting Adverse Events

9.7.1. Recording Adverse Events

To improve the quality and precision of AE data, Investigators should observe the following guidelines:

- Whenever possible, use recognized medical terms when recording AEs on the AE page of the eCRF. Do not use colloquialisms, jargon, or abbreviations.
- If known, record the diagnosis (i.e., disease or syndrome) rather than component signs and symptoms on AE pages of the eCRF (e.g., record "congestive heart failure" rather than "dyspnea", "rales", and "cyanosis"). However, signs and symptoms that are considered unrelated to an encountered syndrome or disease should be recorded as individual AEs on the eCRF page. For example, if congestive heart failure and severe headache are observed at the same time, each event should be recorded as an individual AE.
- Adverse events occurring secondary to other events (i.e., sequelae) should be identified by the primary cause. A primary AE, if clearly identifiable,

generally represents the most accurate clinical term to record on the AE page of the eCRF. If a primary SAE is recorded on an AE eCRF page, events occurring secondary to the primary event should be described in the narrative description of the event.

• Laboratory abnormalities that are identified by the Investigator as clinically significant are to be considered AEs and recorded on the AE eCRF page.

9.7.2. Reporting of Serious Adverse Events

Serious AEs require reporting to the Sponsor or designee within 24 hours, regardless of the relationship of the event to the study treatment regimen. Refer to Section 9.1.7 for the definition of an SAE. Procedures for recording and reporting SAEs will be detailed in a separate Safety Management Plan for processing SAEs, expedited safety reports, and the emergency unblinding of patients.

Within 24 hours of the Investigator's observation or learning of an SAE, the Investigator should notify Pivotal, S.L.U. (Pivotal Pharmacovigilance) by completing the SAE forms as thoroughly as possible with all available details of the event, including a determination of causality (even if preliminary), and signing them. The Investigator should communicate with Pivotal Pharmacovigilance if input is needed to complete the SAE assessment. Investigator causality determination and signature MUST be included for all SAEs. The completed SAE form and cover sheet should be sent by email or fax to Pivotal Pharmacovigilance.

Pivotal Pharmacovigilance

North America: (Fax) [contact]

(Phone) [contact]

Europe/UK/Asia-Pacific: (Fax) [contact]

(Phone) [contact]

e-mail: [contact]

If not all information regarding an SAE is initially available, the Investigator should not wait to receive additional information before completing the AE eCRF and SAE forms. For initial SAE reports, the Investigator should record all case details that can be garnered on the SAE form and the AE eCRF page. Relevant follow-up information is to be submitted on updated SAE forms as soon as it becomes available.

If there are questions regarding reporting an SAE or if information needs to be transmitted that cannot be recorded on the SAE forms (e.g., discharge summaries, laboratory reports), the Investigator should contact Pivotal Pharmacovigilance.

For unexpected serious adverse drug reactions (SUSARs), blinded reports will be disseminated and provided to Investigators at each study site.

When required and according to local law and regulations, unblinded SUSARs or other SAEs will be reported by an unblinded designee to the IRB/EC and regulatory authorities.

9.7.3. Special Reporting Situations

Death

Death is an outcome of an event. The event that resulted in death should be recorded and reported on the SAE form and the AE eCRF page.

Surgical or Diagnostic Procedures

The illness leading to a surgical or diagnostic procedure is to be recorded as an AE/SAE, not the procedure itself. The procedure is to be captured in the case narrative as part of the action taken in response to the illness.

9.7.4. Reporting Pregnancies

Pregnancy itself is not considered an AE. If a **patient becomes pregnant** during the study or **within 1 month of discontinuing** any study medication or the **partner of a patient** participating in the study becomes pregnant during the study or **within 3 months of discontinuing** any study medication, the Investigator should report the pregnancy on a separate pregnancy report form provided to the sites. Only pregnancies occurring from the time of first study medication dose administered to the patient through Day 505 will be reported and documented.

The patient/partner should be followed by the Investigator until completion of the pregnancy. If the pregnancy ends for any reason before the anticipated date, the Investigator should notify the Sponsor. At the completion of the pregnancy, the Investigator will document the outcome of the pregnancy.

This pregnancy report form must be completed and submitted, either by e-mail or fax, immediately but no later than 24 hours of the Investigator's learning of the event to:

Pivotal Pharmacovigilance

North America: (Fax) [contact] Europe/UK/Asia-Pacific: (Fax) [contact]

e-mail: [contact]

However, any pregnancy complication, spontaneous or elective abortion, still birth, neonatal death, or congenital anomaly will be recorded as an AE or SAE, and reported, as applicable.

9.8. Safety Committee

A Safety Committee will conduct regular blinded reviews of all AEs and reactogenicity events. The Safety Committee will also review blinded safety data from a sentinel cohort

of 12 patients before dosing in the expanded cohort of patients. The responsibilities of the Safety Committee will be delineated in a Safety Analysis Plan.

9.9. Data Monitoring Committee

This study will be overseen by an independent DMC, which will have access to unblinded data, as needed, for the assessment of patient safety. A charter describing the roles, responsibilities, and operating procedures of the DMC will be implemented prior to study initiation.

10. STATISTICS

10.1. General Procedures

Baseline is defined as data collected closest to randomization prior to any study medication dosing. All analyses and summary statistics will be presented by treatment group (HepTcell, placebo).

Descriptive statistics, including the numbers and percentages for categorical variables and the numbers, means, standard deviations, medians, minimums and maximums for continuous variables will be provided by treatment.

10.2. Sample Size

A study of IFN-α2 in a population with inactive CHB reported a mean incremental decrease of 1.3 log-qHBsAg at 24 weeks in those patients completing IFN-α2 treatment compared to non-treatment. Mean decrease would translate to approximately 50% of patients completing treatment achieving 1.3 log-qHBsAg response (reduction). To estimate treatment effect in the current study, the proportion of patients achieving a 1.0-log reduction in qHBsAg is estimated as one-half (25% of patients) who achieve this response. Assuming a response rate of 3% on placebo and 25% on HepTcell, 40 patients will be randomized per treatment group to detect a difference in the proportion of patients treated with HepTcell achieving the primary endpoint compared to patient treated with placebo at a 0.05 level of significance (two-sided) with approximately 80% power.

10.3. Analysis Sets

Safety Analysis Set: All patients who receive any study medication. Patients will be analyzed according to the treatment that they receive.

Modified intent to treat (mITT) Analysis Set: All randomized patients who receive any amount of study medication, have a baseline and at least one post-baseline efficacy assessment. Patients will be analyzed according to the treatment that they receive. This analysis set will be used for primary and secondary analyses.

Per Protocol (PP) Set: All randomized patients who receive the full designated amount of study medication according to the correct treatment assignment and who have results from HBV serology and viral markers at Day 85.

10.4. Statistical Methods

10.4.1. Primary Efficacy Endpoint

For the primary analysis, proportions of patients with virologic response, defined as a 1.0-log reduction in HBsAg or serologic clearance of HBsAg, will be compared between HepTcell and placebo groups using Fisher's Exact Test at a 0.05% two-sided level of significance.

Patients who discontinue prematurely or have missing data will be considered nonresponders for that endpoint. Linear and logistic regression will be employed to examine the effects of baseline factors, such as qHBsAg level, HBV DNA levels, and hepatitis B genotype on response.

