6.2. Randomization

Following completion of the Screening activities, patients who meet the all the inclusion and none of the exclusion criteria will be registered by the Interactive Web Response System (IWRS). Eligible patients will be randomly assigned in a 1:1 ratio to HepTcell or placebo treatment groups. Randomization will be stratified by study center to minimize imbalances between treatment groups.

The first 12 patients (6 HepTcell, 6 placebo) will form the sentinel cohort. To assure a 1:1 distribution of HepTcell and placebo in the sentinel cohort, randomization in this group will not be stratified.

If none of the Stopping Rules (see Section 7.1.1) are met in one or more patients in the sentinel cohort, randomization may continue in the expanded study cohort.

The randomization list will be drawn up by an independent statistician.

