5.3 Summary of Statistical Methods

This study is designed as a phase 2 study, exploratory in nature, to evaluate the response to HepTcell in treatment-naïve patients with inactive CHB. Comparisons will be performed between HepTcell and Placebo at a two-sided type I error rate of 0.05 which will not be adjusted for multiple testing.

The study will be considered to have achieved proof-of-concept when the 2-sided p-value is <0.05. Accordingly, the primary and key secondary efficacy endpoints will present 2-sided 95% Confidence Intervals (95%Cls) when applicable.

Unless otherwise specified, efficacy analyses will be performed using the mITT population, where patients will be in the treatment arm to which they received. As described in more detail elsewhere, patients will be analysed according to the treatment of the most treatment received. Moreover, supportive efficacy analyses will be performed in the PP population. Safety related analyses will use the safety population, where patients will be analyzed according to the treatment that they receive.

All applicable baseline data will be summarized by treatment arm (HepTcell, placebo), unless specified otherwise. Safety and efficacy data will also be summarized by treatment arm and additionally by time-point of assessment and/or follow-up, when appropriate.

Continuous variables will be summarized using the number of observations (n), mean (95%CI, if appropriate), standard deviation (SD), Standard error (SE, if appropriate), median, first quartile (Q1), third quartile (Q3), minimum, and maximum along with the total number of patients contributing values.

Descriptive statistics for categorical/qualitative data will include frequency counts and percentages. The denominator for all percentages will be the total number of patients in the treatment arm and dose number (if applicable) within the population of interest, unless stated otherwise in the table footnote.

Change from baseline is calculated only for patients with non-missing values for both the baseline and the time-point of interest and will be missing otherwise.

Statistical comparisons will be performed between HepTcell and placebo at a 5% confidence level.

All relevant patient data will be included in listings. All patients entered into the database will be included in patient data listings. The listings will be generally sorted by treatment arm and then Patient ID, unless specified otherwise.

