5.3.2.1 Primary endpoint

The primary endpoint will be considered as described in section 4.2.1.

Patients who discontinue early or have missing HBsAg values on Day 169 but who achieve virologic response or serologic clearance of HBsAg on the last available assessment prior to Day 169 will be treated as responders for the primary endpoint; otherwise, patients with early discontinuation or missing HBsAg values on Day 169 will be treated as non-responders.

The proportion of patients achieving virologic response (defined as a 1.0-log reduction in HBsAg or serologic clearance of HBsAg) on Day 169 will be estimated as follows:

(Number of patients having achieved virologic response or serologic clearance of HBsAg to Day 169) / (Number of patients in the corresponding treatment (or overall)) x 100%

This proportion will be compared between treatment groups using Chi-Square Test or Fisher's Exact Test at a 0.05% two-sided level of significance. Fisher's Exact Test will be used if the expected values of at least the 80% of the cells in the contingency table created for estimating proportions are lower than 5.

This proportion will be analyzed using logistic regression models with treatment arm and baseline qHBsAg level as covariate. The analysis of maximum likelihood and odds ratio estimates for patients predicting a 'Yes' in achieving virologic response will be shown.

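### Both documents set the primary test at 0.05% (0.0005) two-sided, 100 times stricter than the 0.05 used for sample size and proof of concept; taken literally, power is about 17%

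*Protocol*

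**What the plan says.** Protocol 10.4.1 compares the response proportions by Fisher's "Exact Test at a 0.05% two-sided level of significance". The Study Summary (Efficacy Analyses) has the same words. SAP 5.3.2.1 repeats the percentage for the primary endpoint, although it allows a choice of test: "This proportion will be compared between treatment groups using Chi-Square Test or Fisher"'s exact test. SAP 5.3.2.2.1 (HBsAg clearance) and 5.3.2.2.2 (HBV DNA clearance) repeat it again. Protocol 10.4.2 carries the primary approach over to the categorical secondary and exploratory endpoints.

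Elsewhere the level is different:

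- Protocol 10.2, the Study Summary and SAP 5.1 size the trial "at a 0.05 level of significance (two-sided) with approximately 80% power".
- SAP 5.3 says that comparisons are made "at a two-sided type I error rate of 0.05 which will not be adjusted for multiple testing".
- SAP 5.3 gives the success rule: "The study will be considered to have achieved proof-of-concept when the 2-sided p-value is <0.05".
- SAP 5.3 later says that comparisons use 5% as a confidence level, which is not the same quantity as a significance level.

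**The concern.** 0.05% is 0.0005, and 0.05 / 0.0005 = 100. The operative sentence for the primary test therefore sets a threshold one hundred times stricter than the one the trial was sized for and the one that defines proof of concept.

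The documents' order of precedence does not settle the matter. Protocol 10.6 lets the SAP supersede the protocol on analyses but keeps the primary analysis unchanged. The protocol's primary-analysis section is one of the places that says 0.05%, and the SAP's own primary-endpoint section agrees with it. SAP 5.3.17 lists only the ECG parameters as a change from the protocol, and SAP version 2.0 still carries the wording.

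At stake is the pass/fail rule of the trial. A p-value between 0.0005 and 0.05 meets SAP 5.3 and fails Protocol 10.4.1 and SAP 5.3.2.1.

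**Working it through.** **Inputs.** From Protocol 10.2: "Assuming a response rate of 3% on placebo and 25% on HepTcell, 40 patients will be randomized per treatment group", level 0.05 two-sided, power about 80%. Allocation is 1:1 (Protocol 6.2). Protocol 10.4.1 names Fisher's exact test. No dropout inflation is stated, so 40 per arm is used throughout.

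**Method.** Enumerate all 41 × 41 outcomes (x responders on placebo, y on HepTcell). Weight each by Binomial(40, 0.03) at x times Binomial(40, 0.25) at y. Power is the total weight of the outcomes whose two-sided p-value is below α.

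**Step 1: reproduce the plan's figure at α = 0.05.** Fisher power is 78.0%. As a cross-check, the pooled normal approximation is

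Φ{[|p₁ − p₂|√n − z√(2p̄(1 − p̄))] / √(p₁(1 − p₁) + p₂(1 − p₂))}

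with p̄ = 0.14, √(2 × 0.14 × 0.86) = 0.491, 0.22 × √40 = 1.391, √(0.0291 + 0.1875) = 0.465 and z = 1.960. This gives (1.391 − 0.962) / 0.465 = 0.92, so power is 82.2%. Both values fit the stated figure of about 80%, so the sample size rests on 0.05.

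**Step 2: repeat at α = 0.0005.** Fisher power is 16.7%. In the approximation z becomes 3.481, and (1.391 − 1.708) / 0.465 = −0.68, so power is 24.8%. Fisher power near 80% at this level would need about 88 to 90 per arm (79.9% at 88, 81.4% at 90).

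**Step 3: responders needed on HepTcell for significance, Fisher, 40 per arm.**

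| Placebo responders | α = 0.05 | α = 0.0005 |
|---|---|---|
| 0 | 6 | 11 |
| 1 | 8 | 14 |
| 2 | 9 | 16 |

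**Step 4: how often the two rules disagree.** Under the planned effect, the probability that the Fisher p-value lies between the thresholds is 78.0% − 16.7% = 61.3%. The expected counts are 40 × 0.25 = 10 and 40 × 0.03 = 1.2. An outcome of 10/40 against 1/40 gives p = 0.0069, which falls in that zone.

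**Step 5: the test the SAP would select.** SAP 5.3.2.1 uses Fisher only if at least 80% of the cells have expected counts below 5. With T responders in two arms of 40, the expected counts are T/2 in each responder cell and (80 − T)/2 in each non-responder cell. When responders are few, only the two responder cells can fall below 5, which is 2 of 4 (50%). The rule therefore leads to chi-square. Its exact power is 88.5% at 0.05 and 20.2% at 0.0005, a gap of 68.3 points. The responders needed against 0, 1 or 2 on placebo are 4, 6 or 8 at 0.05, and 11, 13 or 15 at 0.0005.

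**The case against.** The best defence is that the intended level is easy to recover. The sample size works at 0.05 and not at 0.0005. SAP 5.3 gives a type I error rate of 0.05, pairs it with 95% confidence intervals, and is the only place that says when the study succeeds. A stray percent sign after 0.05 is the only plausible reading, so the 17% describes a rule nobody meant to apply. That stands as an account of intent. It does not remove the contradiction, because the percentage appears in five places across both documents, including both primary-endpoint sections.

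A second objection is that 16.7%, and a miss in about five trials of six, belong to Fisher's test in Protocol 10.4.1. Under SAP 5.3.2.1 the test would be chi-square, with 20.2% power and a miss in about four of five. This is correct and narrows the figure slightly; the conclusion is unchanged.

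Third, SAP section 2 and the addendum report that the primary and secondary endpoints were not met at Week 24 and that the study is being terminated. A result that misses 0.05 also misses 0.0005 on the same test, so if 0.05 was applied the discrepancy changed nothing. But the documents do not say which threshold was applied. As written, a missed endpoint could mean p above 0.05 or only p above 0.0005.

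**Conclusion.** The point holds. The level of the primary test is stated as 0.0005 in the sections that define it and as 0.05 in the sample size and the proof-of-concept rule. For 40 per arm at 3% against 25%, Fisher power falls from 78.0% to 16.7% if the primary-analysis wording is followed (from 88.5% to 20.2% with chi-square). In about 61% of trials with the planned effect (68% with chi-square) the two rules give opposite answers. These figures assume the protocol's own response rates, full arms of 40 and no loss to missing data.

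The percentage is very probably a slip for 0.05, and the finding does not show that the trial was underpowered by design. It must still be corrected, because it sits in the sentence that decides whether the primary endpoint is met.

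**What to change.** Replace the 0.05% wording with *two-sided significance level of 0.05 (5%)* in the protocol Study Summary (Efficacy Analyses), Protocol 10.4.1, and SAP 5.3.2.1, 5.3.2.2.1 and 5.3.2.2.2. In SAP 5.3, change the 5% confidence level to a *5% significance level*.

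Because the Week 24 analysis has already been run, make the correction as a dated clarification, and state in the study report which threshold was applied to the primary and secondary endpoints. The cost is wording only: no new data, no change of design and no change to the sample size.
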